## **1.0                   Introduction**

This Statistical Analysis Plan (SAP) describes the statistical analyses for risankizumab Study M16-005 A Multicenter, Single-Arm, Open-Label Study to Assess the Usability of the Risankizumab Autoinjector Combination Product in Adult Patients with Moderate to Severe Plaque Psoriasis. Study M16-005 evaluates the usability of the combination product of risankizumab in an AI and to evaluate the efficacy, safety, and tolerability of risankizumab 150 mg/mL administered by AI for the treatment of adult patients with moderate to severe plaque psoriasis.

This SAP provides summaries of the planned statistical analyses for efficacy and safety endpoints, interim analysis, and overall type-I error control strategies.

There will be no analyses of pharmacokinetic endpoints in this study.

The SAP will not be updated in case of administrative changes or amendments to the protocol unless the changes impact the analysis.

Unless noted otherwise, all analyses will be performed using SAS Version 9.4 (SAS Institute Inc., Cary, NC 27513) or later under the UNIX operating system.

This SAP includes changes to analyses described in the protocol. Details are outlined in Section 13.0.

## **2.0                   Study Design and Objectives**

### **2.1                   Objectives and Hypotheses**

The objectives of this study are to evaluate the usability of the combination product of risankizumab in an AI and to evaluate the efficacy, safety, and tolerability of risankizumab 150 mg/mL administered by AI for the treatment of adult patients with moderate to severe plaque psoriasis.

[figure not shown]
The following key endpoints will be evaluated:

- Proportion of subjects with an Observer rating of successful subject self-administration, defined as any subjects who successfully completed the sequence of 4 critical steps in the Instructions for Use (IFU) without errors to administer study drug via the AI at Week 0 and Week 28
- Proportion of subjects achieving at least 90% improvement from baseline in the Psoriasis Area and Severity Index (PASI) (PASI 90) at Week 16
- Proportion of subjects achieving sPGA clear or almost clear at Week 16
- Proportion of subjects achieving 100% improvement from baseline in PASI (PASI 100) at Week 16
- Proportion of subjects achieving at least 75% improvement from baseline in PASI (PASI 75) at Week 16
- Proportion of subjects achieving sPGA of clear at Week 16.
- Proportion of subjects who had no potential hazards as measured by an Observer on the possible use-related hazards checklist for self-administration with AI at Week 0 and Week 28
- Subject rating of acceptability by the Self-Injection Assessment Questionnaire (SIAQ; Operations Manual Appendix B) at each visit collected.

## 2.2 Study Design Overview

This is a Phase 3 multicenter, single-arm, open-label study that will evaluate usability of the risankizumab-AI combination product. In addition, efficacy will be evaluated by an efficacy assessor. The study includes a 30-day screening period with study visits at Week 0, 4, 16, 28, and 40 with a subsequent follow-up telephone call at approximately 20 weeks after the last dose of study drug (Week 48). Study drug dosing will consist of four self-administered doses given subcutaneously on Weeks 0, 4, 16, and 28. Dosing on Week 4 and Week 16 will be self-administered at home. Efficacy assessments will be performed at each study visit (Weeks 0, 4, 16, 28, and 40).

The schematic of the study is shown in [Figure 1](#).

**Figure 1.** Study Schematic

## 2.3 Treatment Assignment and Blinding

All subjects will receive open-label risankizumab.

## 2.4 Sample Size Determination

This study is designed to enroll approximately 100 subjects who will self-administer the risankizumab-AI combination product at Weeks 0, 4, 16, and 28.

Assuming the point estimate is 90% for the proportion of subjects with an observer rating of successful subject self-administration at Week 28, the current sample size of 100 subjects will provide a 95% confidence interval of  $\pm 5.9\%$  around a point estimate.

In addition, assuming comparable response rates as the Phase 3 pivotal studies, with the current sample size of 100, the PASI 90 rate at Week 16 can be estimated with a 95% confidence interval of  $\pm 8.6\%$  when the point estimate is 74%; and the sPGA of clear or almost clear rate at Week 16 can be estimated with a 95% confidence interval of  $\pm 7.0\%$  when the point estimate is 85%.

## **3.0 Endpoints**

### **3.1 Key Efficacy and Usability Endpoints**

The following key endpoints will be evaluated:

- Proportion of subjects with an Observer rating of successful subject self-administration, defined as any subjects who successfully completed the sequence of 4 critical steps in the IFU without errors to administer study drug via the AI at Week 0 and 28
- Proportion of subjects achieving at least 90% improvement from baseline in PASI (PASI 90) at Week 16
- Proportion of subjects achieving sPGA clear or almost clear at Week 16
- Proportion of subjects achieving 100% improvement from baseline in PASI (PASI 100) at Week 16
- Proportion of subjects achieving at least 75% improvement from baseline in PASI (PASI 75) at Week 16
- Proportion of subjects achieving sPGA of clear at Week 16.
- Proportion of subjects who had no potential hazards as measured by an observer on the possible use-related hazards checklist for self-administration with AI at Week 0 and Week 28
- Subject rating of acceptability by the Self-Injection Assessment Questionnaire (SIAQ) at each visit collected.

### **3.2 Additional Efficacy Endpoints**

All key efficacy endpoints will be analyzed at all other visits collected. Additional variables to be provided will include the proportion of subjects achieving PASI 50, as well as change and percent change from baseline in PASI, at each visit collected.

### **3.3 Safety Endpoints**

The following endpoints will be included in the safety analyses:

- Treatment emergent adverse events (TEAEs);
- Serious adverse events (SAEs);
- Areas of safety interest (ASI);
- Adverse events (AEs) leading to discontinuation;
- Vital signs and laboratory tests.

### **3.4 Additional Endpoints**

There are no additional endpoints planned other than those described above.

## **4.0 Analysis Populations**

The following population sets will be used for the analyses.

The intent-to-treat (ITT) Population, which is defined as all subjects who have at least 1 dose of study drug in Study M16-005, will be used for the efficacy and usability analyses.

The Safety Analysis Population, which is defined as all subjects who received at least 1 dose of study drug in Study M16-005, will be used for all safety analyses. In this study, the safety population is the same as the ITT population.

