**8.0****Efficacy Analyses****8.1****General Considerations**

All summary statistics for the efficacy and usability analysis will be conducted in the ITT Population. No statistical tests will be performed.

All efficacy endpoints will be summarized up to Week 28 during this analysis.

Categorical variables will be summarized by frequencies, percentages, and the 95% confidence intervals (CIs). Continuous variables will be summarized by least square mean, standard error, and the 95% CIs.

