## **8.3 Efficacy and Usability Analysis**

### **8.3.1 Key Usability Analysis**

The following key usability endpoints will be evaluated:

- Proportion of subjects with an Observer rating of successful subject self-administration, defined as any subjects who successfully completed the sequence of 4 critical steps in the Instructions for Use (IFU) without errors to administer study drug via the AI at Week 0 and Week 28
- Proportion of subjects who had no potential hazards as measured by an Observer on the possible use-related hazards checklist for self-administration with AI at Week 0 and Week 28
- Subject rating of acceptability by the Self-Injection Assessment Questionnaire (SIAQ) at each visit collected.

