### **8.3.2 Handling of Missing Data for the Key Usability Analysis**

The key usability endpoints will be summarized by as-observed cases.

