**12.0                   Overall Type-I Error Control**

No statistical tests will be performed in this single-arm, open-label study.

Since there are no efficacy analyses for early stopping planned for the DMC review, no alpha spending is needed due to the DMC review.

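### The at-least-one-dose set used for usability drops a subject whose Week 0 self-injection delivers no drug and who is never dosed later

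*SAP*

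**What the plan says.** SAP Section 4.0 assigns one set to both efficacy and usability: "all subjects who have at least 1 dose of study drug in Study M16-005, will be used for the efficacy and usability analyses". It adds that this set is the same as the safety set, whose members received at least one dose, so having a dose must mean having received one. Section 8.1 repeats the restriction: "All summary statistics for the efficacy and usability analysis will be conducted in the ITT Population".

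Section 2.2 states that "Study drug dosing will consist of four self-administered doses given subcutaneously on Weeks 0, 4, 16, and 28", so the first dose is itself a self-injection. Section 8.3.1 makes that event an outcome at Week 0 and again at Week 28. The first-listed key usability endpoint counts subjects who "successfully completed the sequence of 4 critical steps in the Instructions for Use (IFU) without errors to administer study drug via the AI". The second is "Proportion of subjects who had no potential hazards as measured by an Observer on the possible use-related hazards checklist for self-administration with AI".

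For missing data, Section 8.3.2 says: "The key usability endpoints will be summarized by as-observed cases". Section 8.2 says the same. No attempt-based usability set is defined anywhere in the SAP.

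**The concern.** A set of subjects with at least one dose is ordinary for efficacy and safety. For Week 0 usability it is circular, because receiving the first dose is closely tied to whether the self-administration worked. The subject with the most serious usability outcome, an attempt in which no drug is delivered and no dose ever follows, is the one removed.

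At stake is the Week 0 part of the first-listed key endpoint of a usability study, and the Week 0 no-hazard proportion, which loses the same subject. If the dropped attempts are mostly rated failures, the reported success rate is too high and its interval is narrower than it should be.

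**Working it through.** **Who is excluded.** Three conditions must all hold: an observed Week 0 attempt, no drug received at Week 0, and no dose at any later time. A subject who makes an error but receives drug is in the ITT set. So is a subject who fails at Week 0 and is dosed later. Week 28 is essentially unaffected, because a subject observed there would have to have missed every earlier dose and then also receive none at Week 28.

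**Whether another rule restores the subject.** The as-observed rule governs missing assessments. Section 8.1 places all usability summaries inside the ITT set, so a rating that was recorded for a never-dosed subject is still left out. Disposition (Section 5.0) starts from treated subjects and has no line for subjects who attempted but were not dosed, so the exclusion may not be visible there either.

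**Inputs.**
- Sample size: 100 (Section 2.4).
- Success rate: 90%. Section 2.4 states it for Week 28 ("Assuming the point estimate is 90% for the proportion of subjects with an observer rating of successful subject self-administration at Week 28"). Applying it to Week 0 is an assumption, varied below.
- Number of such subjects, k: not given, and may be zero.

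**The plan's own figure.** Half-width = 1.96 × √(p(1 − p)/n) = 1.96 × √(0.90 × 0.10/100) = 5.88 points. This agrees with the stated ±5.9. The lower limit is 90.00 − 5.88 = 84.12%.

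**One subject dropped (k = 1), starting from 90/100.**
- Attempt rated a failure: 90/99 = 90.91%, a shift of +0.91 points. Half-width 5.66, lower limit 85.2%.
- Attempt rated a success: 89/99 = 89.90%, a shift of −0.10 points. Half-width 5.94, lower limit 83.96%.

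**Direction.** Let f be the probability that a dropped attempt would be rated a failure. The mean shift is 0.909f − 0.101(1 − f). It is zero at f = 0.101/(0.909 + 0.101) = 10%, which is the failure rate in the full set. Above that, the exclusion raises the rate on average.

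**Other assumed Week 0 rates, k = 1.**

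| Full set | Drop one failure | Drop one success | Break-even f |
|---|---|---|---|
| 80/100 | 80/99 = 80.81% (+0.81) | 79/99 = 79.80% (−0.20) | 20% |
| 90/100 | 90/99 = 90.91% (+0.91) | 89/99 = 89.90% (−0.10) | 10% |
| 95/100 | 95/99 = 95.96% (+0.96) | 94/99 = 94.95% (−0.05) | 5% |

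**More than one subject, from 90/100, all rated failures.** k = 2 gives 90/98 = 91.8%, and k = 3 gives 90/97 = 92.8%. These counts only show how the shift grows. Nothing in the SAP suggests that they will occur.

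No size is computed for the no-hazard proportion, because the SAP gives no assumed rate for it. Its direction depends on what the observer recorded at the undelivered attempt.

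**The case against.** The strongest reply is that the case is hypothetical. Whether it can arise depends on what happens after an undelivered injection and on what is recorded as a dose. The protocol or operations manual may settle both, and neither is at hand. If such subjects are dosed afterwards, they stay in the set and the gap closes. The SAP states its population clearly and uses it consistently, so there is no contradiction. The effect is under 1 point per subject on a descriptive rate, and Section 12.0 confirms the absence of any decision rule: "No statistical tests will be performed in this single-arm, open-label study". The one precision statement for self-administration concerns Week 28.

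Most of this stands, and it limits the point to a minor one. The direction is also not certain. The endpoint is an observer rating of four error-free steps, and a device malfunction without user error might not be rated a failure.

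The reply does not show that the exclusion is harmless when the case does occur. It then follows from a stated rule in Sections 4.0 and 8.1, not from detail left to another document. An analysis set fixed in advance should not depend on the outcome it is used to measure.

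**Conclusion.** The concern holds as a minor design point. Under Sections 4.0 and 8.1, a subject who attempts the Week 0 self-injection, receives no drug and is never dosed later is left out of both Week 0 observer endpoints, and no other section brings the subject back.

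At an assumed Week 0 rate of 90% in 100 subjects, each such subject moves the success rate by +0.91 points if rated a failure or −0.10 if rated a success. With no such subject, the effect is zero. An upward shift is likely, since it requires only that more than about 10% of the dropped attempts would be rated failures, but it is not assured. The size rests on applying the Week 28 rate to Week 0 and on an unknown number of subjects. The SAP's ±5.9 points is correct.

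**What to change.** In Sections 4.0 and 8.1, define the set for the Week 0 usability endpoints as all enrolled subjects who attempted self-administration with the autoinjector, whether or not drug was delivered. Use the observer's recorded rating and hazard result as they stand, without recoding undelivered attempts as failures. Keep the dosed set for efficacy and safety.

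The cost is a short change of wording in those two sections. A count of attempts in the Section 5.0 disposition summary would make the new denominator traceable. The reported Week 0 rate may be slightly lower. The observer record for undelivered attempts must be available in the database, and the SAP does not show whether it is. Sample size and the efficacy and safety analyses do not change.

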## **5.0                   Subject Disposition**

The total number of subjects who were treated, completed, and discontinued will be summarized.

A summary of subject accountability will be provided where the number of subjects in each of the following categories will be summarized:

- Subjects who received at least one study drug;
- Subjects who completed study;
- Subjects who discontinued study drug (all reasons and primary reason);
- Subjects who discontinued study (all reasons and primary reason)

For end of study participation, the number and percentage of subjects who completed this study (or did not with associated reasons) will be summarized overall.

## **6.0                   Study Drug Duration and Compliance**

Duration of treatment is defined for each subject as last dose date minus first dose date + 84 days. Duration of treatment will be summarized using the number of subjects treated, mean, standard deviation, median, minimum and maximum.

Treatment compliance will be summarized for the entire treatment period and each study drug administration visit for the ITT population.

There will be a summary of the number of subjects receiving study drug and dose at each study drug administration visit. This will be repeated on the cumulative number of doses.

When computing compliance at each study drug administration visit, the denominator will include all subjects in each analysis population who have not prematurely discontinued the study drug prior to the scheduled study drug injection.

## **7.0 Demographics, Baseline Characteristics, Medical History, and Prior/Concomitant Medications**

### **7.1 Demographics and Baseline Characteristics**

Continuous demographic variables include age, weight, height, and body mass index (BMI). Categorical demographic variables include sex, ethnicity, race, age (< 40, 40 – 65,  $\geq$  65 years), weight ( $\leq$  100 or  $>$  100 kg), BMI ( $<$  25,  $\geq$  25 –  $<$  30,  $\geq$  30 kg/m^2), tobacco user (current, former, never, unknown), and alcohol user (current, former, never, unknown).

Disease characteristics include prior systemic biologic for psoriasis (0 vs.  $\geq$  1), PASI (Psoriasis Area and Severity Index), BSA (Body Surface Area), sPGA categories, history of psoriatic arthritis (yes, no), duration of plaque psoriasis (in years).

Demographics and baseline characteristics will be summarized for the ITT Population. Categorical variables will be summarized with the number and percentage of subjects based on the number of non-missing observations. Continuous variables will be summarized with descriptive statistics (number of non-missing observations, mean and standard deviation, median, minimum and maximum).

### **7.2 Medical History**

Medical history data will be coded using the Medical Dictionary for Regulatory Activities (MedDRA). The actual version of the MedDRA coding dictionary will be noted in the statistical tables and clinical study report. The number and percentage of subjects in each medical history category (by MedDRA system organ class and preferred term) will be summarized overall. The system organ class (SOC) will be presented in alphabetical order, and the preferred terms will be presented in alphabetical order within each SOC. Subjects reporting more than one condition/diagnosis will be counted only once in each corresponding category (SOC or preferred term).

Medical history will be summarized among the ITT Population.

**7.3****Prior and Concomitant Medications**

Prior and concomitant medications will be summarized by generic name. A prior medication is defined as any medication taken prior to the date of the first dose of study drug. A concomitant medication is defined as any medication that started prior to the date of the first dose of study drug and continued to be taken on or after the first dose of study drug or any medication that newly started on or after the date of the first dose of study drug, but not after the date of the last dose of study drug plus 28 days. The number and percentage of subjects taking medications will be summarized by generic drug name based on the World Health Organization (WHO) Drug Dictionary for both prior and concomitant medications.

In addition, subjects' prior biologic therapy for psoriasis will also be summarized by the reason for discontinuation.

Prior and concomitant medications will be summarized among the ITT Population.

**8.0****Efficacy Analyses****8.1****General Considerations**

All summary statistics for the efficacy and usability analysis will be conducted in the ITT Population. No statistical tests will be performed.

All efficacy endpoints will be summarized up to Week 28 during this analysis.

Categorical variables will be summarized by frequencies, percentages, and the 95% confidence intervals (CIs). Continuous variables will be summarized by least square mean, standard error, and the 95% CIs.

**8.2****Handling of Missing Data**

Missing data will be imputed using the following methods for the efficacy analyses:

- Non-Responder Imputation (NRI): The NRI analysis will categorize any subject who does not have evaluation during a specific visit window as a non-responder for that visit. The exceptions are: (1) if the subject is a responder both before and after a specific visit window in the particular period, then the subject will be categorized as a responder for the visit; (2) when the subject missed a visit due to COVID-19 pandemic, the missing assessment from that visit will be imputed using Multiple Imputation (MI) to determine the corresponding response status. In present study, only Week 28 or later visits may be affected by the COVID-19 pandemic. The NRI will be the primary missing data imputation approach in the analyses of categorical variables.
- Modified-NRI: Patients who discontinue study drug due to lack of efficacy or due to AE of worsening of psoriasis and do not have Week 16 measurements will be counted as non-responders. Other patients will be summarized using as-observed data. The modified-NRI analysis will be the sensitivity approach to handle missing data in the analysis of key efficacy endpoints specified in Section 3.1.
- As-observed: The as-observed analysis will include all available assessments on a scheduled visit. No missing assessments will be imputed. The as-observed analysis will be the sensitivity approach to handle missing data in the analysis of the key efficacy endpoints specified in Section 3.1.
- Mixed-effect Model Repeat Measurement (MMRM): The repeated measures analysis will be conducted using a mixed model including baseline value and observed measurements at all post-baseline visits, using all available data even if a subject has missing data at some post-baseline visits. The mixed model includes visit as the covariate. An unstructured variance covariance matrix will be used. Parameter estimation is based on the assumption of data being missing at random and using the method of restrictive maximum likelihood (REML). MMRM will be the primary approach in the analysis of continuous variables.

The key usability endpoints will be summarized by as-observed cases.

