## **8.4 Key Efficacy Analysis**

The following key efficacy endpoints will be evaluated:

- Proportion of subjects achieving PASI 90 at Week 16
- Proportion of subjects achieving sPGA clear or almost clear at Week 16
- Proportion of subjects achieving PASI 100 at Week 16
- Proportion of subjects achieving PASI 75 at Week 16
- Proportion of subjects achieving sPGA of clear at Week 16.

Key efficacy endpoints at Week 16 will be analyzed using NRI method to handle missing data. Modified-NRI analysis and as-observed analysis will also be performed to handle missing data as sensitivity analyses.

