## 14.0 References

## **Appendix A. Protocol Deviations**

The number and percentage of subjects who reported at least one of the following protocol deviation categories will be provided.

- Subject entered into the study even though s/he did not satisfy entry criteria.
- Subject developed withdrawal criteria during the study and was not withdrawn.
- Subject received wrong treatment or incorrect dose of study.
- Subject took prohibited concomitant medication.

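### When Week 16 is measured, all three planned analyses score it even after stopping for lack of efficacy or starting other therapy, and the sensitivity set cannot show the effect

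*SAP*

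**What the plan says.** SAP Section 2.1 gives as one objective to "evaluate the efficacy, safety, and tolerability of risankizumab 150 mg/mL administered by AI". Section 8.4 names the primary approach for the Week 16 response endpoints: "Key efficacy endpoints at Week 16 will be analyzed using NRI method to handle missing data". Modified-NRI and as-observed are the sensitivity analyses.

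Section 8.2 defines the three rules:

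- **NRI:** "The NRI analysis will categorize any subject who does not have evaluation during a specific visit window as a non-responder for that visit". There are two exceptions. A subject who responded both before and after the missed window is counted as a responder (a bridged visit). Visits missed because of COVID-19 are multiply imputed, but the SAP says only Week 28 or later can be affected.
- **Modified-NRI:** the rule names a group by its reason for stopping: "Patients who discontinue study drug due to lack of efficacy or due to AE of worsening of psoriasis". It then adds a second condition, that the visit is missing, before failure is assigned: "and do not have Week 16 measurements will be counted as non-responders. Other patients will be summarized using as-observed data".
- **As-observed:** "The as-observed analysis will include all available assessments on a scheduled visit. No missing assessments will be imputed".

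The ITT population (Section 4.0) keeps every dosed subject. Section 5.0 tabulates "Subjects who discontinued study drug (all reasons and primary reason" separately from leaving the study. Appendix A counts as a deviation category "Subject took prohibited concomitant medication". No section links stopping the drug, or use of another therapy, to response status when a measurement exists.

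**The concern.** Under all three rules a subject becomes a non-responder by imputation only if the visit is missing. Modified-NRI looks as if it treats stopping for lack of efficacy as failure, but its second condition makes it a missing-data rule only. A subject who stops because the drug is not working, starts another psoriasis therapy, attends Week 16 and then meets PASI 90 would count as a responder in every analysis.

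Any such response can only raise the rate. The study has a single arm, so no control group carries the same effect. A reader who sees three similar rates could take them as evidence of robustness on a question that none of them addresses.

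**Working it through.** **1. The plan's own precision.** Inputs from SAP Section 2.4: N = 100, PASI 90 of 74%, sPGA clear or almost clear of 85%. Half-width = 1.96 × √(p(1 − p)/N).

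- PASI 90: 1.96 × √(0.74 × 0.26/100) = 8.6 points (stated 8.6).
- sPGA clear or almost clear: 1.96 × √(0.85 × 0.15/100) = 7.0 points (stated 7.0).

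**2. How each rule scores a subject at Week 16.**

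| Subject | NRI | Modified-NRI | As-observed |
|---|---|---|---|
| Stopped for lack of efficacy or worsening, not measured | Non-responder* | Non-responder | Left out |
| Stopped for lack of efficacy or worsening, measured | Measured result | Measured result | Measured result |
| Started another therapy, measured | Measured result | Measured result | Measured result |
| Not measured, any other reason | Non-responder* | Left out | Left out |

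*Unless bridged. Rows two and three are the gap.

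**3. Direction of the sensitivity analyses.** Let R = observed responders, M = subjects missing Week 16, and L = those among M who had stopped for lack of efficacy or worsening. Without bridged visits:

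- NRI = R/N
- Modified-NRI = R/(N − M + L)
- As-observed = R/(N − M)

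Since 0 ≤ L ≤ M, NRI ≤ modified-NRI ≤ as-observed. If M = 0, all three are identical, however many measured subjects had stopped or switched. With B bridged visits NRI becomes (R + B)/N and the ordering can break, but bridging does not address rows two and three either.

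**4. Size.** Let k be the number of measured Week 16 responders who had stopped for these reasons or switched. The SAP does not give k; 0 to 5 is an assumption. The table recodes k of 100 as non-responders (rate with 95% CI by the formula above).

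| k | PASI 90 | sPGA clear or almost clear |
|---|---|---|
| 0 | 74% (65.4–82.6) | 85% (78.0–92.0) |
| 1 | 73% (64.3–81.7) | 84% (76.8–91.2) |
| 2 | 72% (63.2–80.8) | 83% (75.6–90.4) |
| 3 | 71% (62.1–79.9) | 82% (74.5–89.5) |
| 5 | 69% (59.9–78.1) | 80% (72.2–87.8) |

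**5. Illustration with assumed counts.** N = 100, R = 74, M = 4, L = 1. Two of the 74 responders had stopped for lack of efficacy or worsening. No one else is affected.

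- NRI: 74/100 = 74.0%
- Modified-NRI as planned: 74/(100 − 4 + 1) = 74/97 = 76.3%
- As-observed: 74/(100 − 4) = 74/96 = 77.1%
- Modified-NRI with the two recoded: 72/97 = 74.2%

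The planned analyses move only upward from 74.0%. The effect of the two subjects, 2/97 = 2.1 points, shows only when the two versions of modified-NRI are compared.

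**6. Dates.** Doses before the Week 16 visit fall at Weeks 0 and 4 (Section 2.2).

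- Section 6.0 runs treatment duration to 84 days after the last dose: 4 + 84/7 = Week 16 for a subject last dosed at Week 4, and Week 12 for one dosed only at Week 0.
- Section 7.3 excludes from concomitant medication anything started more than 28 days after the last dose: 4 + 28/7 = Week 8, or Week 4 if only the first dose was given. A therapy started between then and Week 16 is outside that table.

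**The case against.** The strongest defence is that Section 8.2 concerns missing data, and that using observed values in all dosed subjects, whatever happened after dosing, is a coherent treatment-policy approach. That stands for the primary NRI, and nothing here requires changing it. It does not supply a sensitivity analysis that looks at drug failure when the subject is still measured.

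Other parts of the defence also stand:

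- A reader might infer that all three analyses always score these subjects on Week 16 data. They do so only when a measurement exists. Otherwise NRI (bridging aside) and modified-NRI count failure, and as-observed leaves the subject out.
- A reader might infer that the SAP expects subjects to switch therapy and be counted as responders. It does not say so. Separate disposition counts and a deviation category make the case possible, not expected. The protocol, not at hand, may limit visits or therapy after stopping.
- A reader might treat 74% and 85% as benchmarks that the study must match. Section 2.4 uses them only to show precision, and no hypothesis tests are planned.
- A subject dosed at Week 4 is still within the 84-day treatment duration at Week 16, so stopping alone does not make that response clearly off-treatment. Other therapy is the stronger worry.

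**Conclusion.** The point holds in a limited form. When a Week 16 measurement exists, all three analyses of the key Week 16 endpoints use it, regardless of earlier stopping for lack of efficacy or worsening, or of another psoriasis therapy. Bridged visits aside, neither sensitivity analysis can fall below NRI, so the set does not test the primary result in the unfavourable direction.

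The size is about 1 point per affected responder at N = 100. An assumed 1 to 5 gives 1 to 5 points, inside the half-widths of 8.6 and 7.0 points; with none, nothing changes. The documents do not show that any bias will occur, or that the primary analysis is wrong. This is a cheap improvement to the sensitivity set.

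**What to change.** In SAP Section 8.2, revise modified-NRI or add one sensitivity analysis along these lines: subjects who, before the Week 16 assessment, start a prohibited psoriasis therapy, or discontinue study drug for lack of efficacy or an adverse event of worsening psoriasis, are Week 16 non-responders whether or not a measurement exists; all others are analysed as observed. Adding it beside the planned modified-NRI would let the difference be read directly.

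Two details matter:

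- Keep the timing condition. Simply removing the missing-measurement condition from the present rule would also turn subjects who stop after Week 16 into Week 16 failures.
- Identify other therapy by its start date relative to the Week 16 assessment, not by the Section 7.3 concomitant window, which closes 28 days after the last dose.

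Leave the primary NRI and the as-observed analysis unchanged. The cost is one rule and a flag built from disposition and medication dates. One sensitivity rate may be slightly less favourable, and some subjects still within the 84-day treatment duration would be counted as failures, which the report should say.
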